5.2 Sample Size

Sample size estimation was based on effect sizes from Barclay & Barclay (2014) who found that CES reduced subjective anxiety with an effect size of $f = 0.47$. Using GPower, the total sample size was estimated to be 38 to achieve power of 0.80 with an alpha criterion of 0.05. Our goal is therefore 40 complete data sets, with 20 participants in each of the two groups.

6.0 Procedures Involved:

We will use a double-blind, placebo-controlled design with random assignment of participants to one of two experimental groups: Active versus Sham CES. Two versions of the critical learning and virtual reality tasks have been developed (Brunyé & Giles, 2023; used in DEVCOM Armament Center IRB protocol 18-007, Tufts University protocol 1808016), and will be used herein, in balanced order across participants.

Military participants will be transported to and from the CABCS research performance site in Medford, MA, for participating in the baseline and follow-up session. If overnight accommodations are required for Soldiers, those will be provided along with other travel related items (e.g., per diem). Travel will be planned by the research team and coordinated with unit leadership (if troop request) or HRVPO (if HRVs). Civilian participants will not be provided with transportation, accommodations, or any other travel-related compensation.

All non-disposable devices used in the protocol will be disinfected in accordance with Occupational Health and Safety Administration and Centers for Disease Control

guidance, and product label instructions, paying attention to the required personal protective equipment and the contact time needed to achieve disinfection. In addition, all frequently touched surfaces in the research area, such as workstations, countertops, and doorknobs will be cleaned between participants.

Upon scheduling, participants will be randomly assigned to the Active or Sham CES condition, using the [=rand()] function in Microsoft Excel. All participants will complete a Thresholding & Baseline session, the CES administration sessions, and then a Follow-up session.

Testing Day 1: Thresholding & Baseline

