alleviate most side effects in most circumstances. Specifically, we will provide successive 5-minute secondary CES administrations at the individualized intensity. After each secondary CES administration, there will be a 1-minute break when the participant will again complete the CES side effects questionnaire. The successive 5-minute CES administrations with interleaved CES side effects questionnaire will be repeated up to twice, or until the negative sensations subside (i.e., all ratings ≤ 3), whichever occurs first. The number of secondary CES administrations necessary to resolve vestibular sensations or anxiety (i.e., 1 or 2) will be recorded by the experimenter. If the participant's reported symptoms do not subside with secondary CES administration, and this occurs for two consecutive CES sessions, they will be withdrawn from the study. Participants will then be dismissed until their next session.

Below is an example schedule for a CES session:

0800-0810	Questionnaires (daily checklist, STAI-S)
0810-0830	CES Administration
0830-0835	Side Effects Questionnaire
0835-0850	Secondary CES Administration (as necessary)
0850-0900	STAI-S Questionnaire
0900	Dismissal

Our goal is to have each participant complete a total of 20 CES sessions, though we do expect some attrition (see Section 3.0). We will prioritize the number of sessions (i.e., reaching 20) over the duration of the study; for example, some participants may complete the 20 sessions study in a 5-week period (rather than 4-week period) due to scheduling issues. We will allow up to 6 weeks to complete the study; if the 20 sessions are not completed in 6 weeks, the participant will be removed from the study. Variability in completion time (i.e., inter-session lag) will be recorded and used as a covariate in statistical analyses.

At the end of the final CES session (session 20), participants will complete the Final CES Session Questionnaire (Appendix A) to assess whether our blinding was successful, and their opinions about CES.

Final Testing Day: Follow-up

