The final testing day will serve as the follow-up session to assess whether 20 sessions of Active (versus Sham) CES will impart any changes to the biochemical, physiological, affective, or behavioral responses to stress induction. This session will be held at approximately the same time of day as the thresholding and baselining session, within 5 days of the last daily CES session. The procedures for this session will precisely match the thresholding and baselining session but without the thresholding phase. After completing the final testing day, participants will have completed the study.

Data Analysis

We will analyze data from our biochemical, physiological, affective, and behavioral measures using Generalized Estimating Equations (GEEs) and/or Analyses of Variance (ANOVAs) to examine changes over the 20 CES sessions, changes from baseline to follow-up, and changes due to Active versus Sham CES. An effect will be deemed statistically significant if the likelihood of its occurrence by chance is $p < 0.05$; to reduce the likelihood of a Type I error, any follow-up comparisons (e.g., t-tests) will use a Bonferroni-corrected alpha criterion.

6.1 Additional Safeguards for Special Populations:

This research is funded by the Department of Defense, and the funding agency is interested in how military personnel respond to CES administration; for that reason, we will prioritize the recruitment of military personnel, and secondarily recruit from civilian populations as required to fulfill our sample size goal.

When recruiting military personnel to participate in this research, we will conform to additional safeguards for the protection of human subjects outlined in DoD Instruction (DoDI) 3216.02. These include additional safeguards to protect participants who may be more vulnerable to coercion or undue influence.

7.0 Investigational Medical Devices:

For the CES sessions, we will be using the Alpha-Stim AID cranial electrotherapy stimulator (CES) medical device, which is an FDA cleared, handheld medical device used for the treatment of anxiety, insomnia, and depression (i.e., AID; see Appendix D).

Because our study is using the device with healthy participants, the device is being used off-label in a manner that is for *investigational use only*. As detailed in the Informed Consent Form, this means that the device is being used in a study examining its safety or effectiveness, and not for the treatment, diagnosis, or prevention of any disorder.

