Cognitive & Affective Responses to CES. To evaluate the cognitive and affective responses to CES, we will use mixed ANOVAs to assess the effect of CES Group (2: Active, Sham) and Session (2: Baseline, Follow-up) on each of four cognitive outcome measures, and one affective outcome measure. Cognitive measures include RMT overall accuracy, SOT absolute angular direction error, SOT absolute distance estimate error, DMT discriminability (d'), and DMT response criterion (c). Affective measures include STAI-S scores, and we will use a mixed ANOVA to assess the effect of CES Group (2: Active, Sham), Session (2: Baseline, Follow-up), and Time (pre-task, 0-min, 20-min, 40-min, 60-min post-task).

Mixed ANOVAs will be conducted using package *rstatix* (ver. 0.7.0; Kassambara, 2023) in R (ver. 4.1.2). Mixed ANOVA assumptions will be checked using package *rstatix* (ver. 0.7.0; Kassambara, 2023) in R (ver. 4.1.2). Extreme outliers will be identified, removed, and mean imputed. Normality will be assessed with Shapiro-Wilk Normality Test; non-normal data will be log-transformed. Homogeneity of variance will be assessed with Levene's Test and confirmed all groups had the same or similar variance. Mauchly's test of sphericity will be automatically conducted and corrected for in the mixed ANOVAs analysis.

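### The counterbalanced task versions have no term in the cognitive ANOVAs, so any difference in difficulty between versions stays in the error of the Group by Session test

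*Protocol*

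**What the plan says.** Protocol section 6.0 (opening paragraph) states: "Two versions of the critical learning and virtual reality tasks have been developed". These are to be used "in balanced order across participants". The documents do not say whether order is also balanced within Active and within Sham. Assignment to arm uses a spreadsheet random-number function, and no stratification is mentioned.

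The SAP (Cognitive & Affective Responses to CES) specifies "mixed ANOVAs to assess the effect of CES Group (2: Active, Sham) and Session (2: Baseline, Follow-up") for the cognitive outcomes. It lists these as follows: "Cognitive measures include RMT overall accuracy, SOT absolute angular direction error, SOT absolute distance estimate error, DMT discriminability (d'), and DMT response criterion (c"). There is no version or order term.

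Nothing elsewhere supplies one. The Data Analysis part of Protocol section 6.0 allows GEEs or ANOVAs and names no such factor. The only covariate the Protocol names is the time taken to complete the sessions: "Variability in completion time (i.e., inter-session lag) will be recorded and used as a covariate in statistical analyses". Neither document says that the two versions are equally difficult.

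**The concern.** Counterbalancing stops a version difference from being mistaken for a session effect. It does not remove that difference from individual change scores. If one version is harder, participants who meet it second appear to decline, and those who meet it first appear to improve. A model with Group and Session alone puts this spread into the residual.

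The Group by Session term is the natural test of H4 (better performance under Active CES), so that test loses precision. Two further effects follow:

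- If order happens to be uneven between arms, part of the version difference moves into the treatment contrast of that one trial.
- If order is even within arms but left out of the model, the error term is too large for the contrast, and the test rejects less often than its nominal 5%.

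Balance set at enrolment may also not survive to analysis. Section 3.0 expects 40-50% attrition, with up to 100 enrolled for 40 complete data sets, and section 16.0 excludes the data of withdrawn participants.

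**Working it through.** **Inputs.** Protocol section 5.2 gives f = 0.47 (from a study of subjective anxiety), alpha 0.05, power 0.80, a total of 38, and a target of 40 (20 per arm). The version difference v is an assumption, shown as a range.

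**1. Reproduce the stated sample size.** For a two-group one-way ANOVA, the F test has 1 and N − 2 df and noncentrality λ = N f², with f² = 0.2209.

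- N = 36: λ = 7.95, power 0.782
- N = 38: λ = 8.39, power 0.805
- N = 40: λ = 8.84, power 0.826

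The stated 38 is recovered as a two-group comparison of an anxiety effect. The documents give no separate power calculation for a cognitive Group by Session test.

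**2. Where the version difference goes.** With two sessions, the Group by Session test equals a two-group test on the change score (Follow-up minus Baseline). Write the change as

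D = μ + d·g + v·s + e,

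where g is the arm (0 or 1), s = +1 or −1 by version order, and SD(e) = 1. With half the participants in each order, leaving s out raises the error variance from 1 to 1 + v². The effective effect size becomes f/√(1 + v²), so λ = 8.836/(1 + v²) at N = 40.

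**3. Power at N = 40, taking f = 0.47 as the effect on the change score (illustrative).**

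| v | 1 + v² | λ, order omitted | Power, order omitted | N for 80%, order omitted |
|---|---|---|---|---|
| 0 | 1.0000 | 8.84 | 0.826 | 38 |
| 0.25 | 1.0625 | 8.32 | 0.802 | 40 |
| 0.5 | 1.2500 | 7.07 | 0.736 | 48 |
| 0.75 | 1.5625 | 5.66 | 0.640 | 58 |
| 1.0 | 2.0000 | 4.42 | 0.535 | 74 |

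With order in the model, power is 0.825 on 37 error df, or 0.824 on 36 if Group by Order by Session is also fitted, whatever v is. These two figures assume order is even within arms. In simulation (20,000 runs per setting) with order even only overall, chance overlap between arm and order costs about one further point: at v = 0, 0.812 with the term against 0.823 without. At v = 0.5 the same comparison is 0.816 against 0.737.

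**4. Type I error (same simulation).**

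| How order is balanced | v | Order omitted | Order modelled |
|---|---|---|---|
| Overall only | 0.5 | 0.052 | 0.050 |
| Overall only | 1.0 | 0.050 | 0.048 |
| Within each arm | 0.5 | 0.030 | 0.050 |
| Within each arm | 1.0 | 0.005 | 0.050 |

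In the within-arm case the version difference cancels from the contrast but stays in the error term, so the test is conservative.

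**5. Chance imbalance.** With 20 participants in each order overall and 20 per arm, the hypergeometric probability of a 12-8 or worse split within an arm is 34%, and of 13-7 or worse 11%. A 13-7 split in one arm means 7-13 in the other. The unadjusted contrast then shifts by v × [(13 − 7)/20 − (7 − 13)/20] = 0.6v. At v = 0.5 this is 0.3 SD, against d = 2f = 0.94.

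**The case against.** The strongest reply is that no harm has been shown. The versions were developed as a pair and used in an earlier protocol. Participants also train to at least 80% accuracy on the map, the target list and the friend-or-enemy stimuli before testing, which should narrow any difference. At v = 0 nothing is lost, and at v = 0.25 the loss is about two points of power. This stands as a limit on size. It does not show that the versions are equal, because the training criterion controls learning accuracy and not difficulty at test under stress.

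Several stronger readings are tempting, and the documents do not support them:

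- **The cognitive test is biased or invalid.** Assignment to arm is random, so there is no average bias. Simulated type I error without the order term is at or below about 0.05.
- **Order is balanced overall but not within arms.** The Protocol is silent on this. Balance within arms is not stated, and neither is its absence.
- **Planned power for H4 falls to 0.54.** No power was planned for H4. The 0.47 is an anxiety effect, and v = 1.0 has no basis in the documents.
- **The follow-up text settles which version is used when.** The sentence "The procedures for this session will precisely match the thresholding and baselining session" does not mention versions. One version per session is a reasonable inference from the phrase about balanced order, and it should be made explicit.
- **The physiology, saliva and STAI-S models have the same defect.** Section 6.0 has errors trigger shocks, so a harder version could produce more of them. Whether that would matter for these outcomes is conjecture, and nothing in the documents quantifies it.

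**Conclusion.** The omission is real: the trial counterbalances a factor and then leaves it out of the analysis that the factor can disturb. The consequence is lost precision in the cognitive Group by Session tests, plus exposure to a chance imbalance of order in a single trial. The loss ranges from nil, if the versions are equally difficult, to about 9 points of power at v = 0.5 (0.826 to 0.736) and 29 points at v = 1.0 (0.826 to 0.535).

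These figures rest on three assumptions: one version per session, an equal overall split of order, and the anxiety-based f = 0.47 applied to a cognitive change score. They illustrate the effect and are not a forecast. The case for acting is that protection costs about one point of power at most, while the possible loss is unknown and could be several times larger.

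**What to change.** 1. In the SAP, add Version Order (AB or BA) as a between-subject factor, with its interaction with Session, to each cognitive ANOVA. It is the Order by Session term that removes the version difference. The cost is 1 error df, or 2 if Group by Order by Session is also fitted: 0.1 to 0.2 points of power when order is even within arms, and about 1 point when it is even only overall.
2. State in the Protocol that each participant receives one version at Baseline and the other at Follow-up, and record the order in the analysis data set.
3. If allocation is still open, balance order within each arm by making it part of the allocation list. The documents do not give enrolment status, and the SAP (May 8, 2025) is two years later than the IRB approval (April 19, 2023), so this step may no longer be possible. Step 1 does not depend on it.
4. Optionally, repeat the physiology, saliva and STAI-S models with the order term as a sensitivity analysis, because errors trigger shocks.

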The baseline session is designed to establish each participant's CES individualized threshold and their baseline stress responsiveness and performance in our virtual reality scenario. This session will always take place at a consistent time of day for individual participants (e.g., morning or afternoon), and always at the CABCS in Medford, MA, using the Soldier and Small Unit Ambulatory Virtual Environment (SUAVE) facility.

Participants will first complete the demographics form, daily participant questionnaire, and emotional state (STAI-S, STAI-T; see Appendix A) questionnaires.

Because our individualized thresholding procedure may result in immediate exclusion from the study, participants will do it prior to baselining.

CES Individualized Thresholding: Participants will be asked to sit and relax in a chair, and we will assist them in donning the CES electrodes on the Alpha-Stim AID device (see Appendix D for specifications). The device has two electrode clips that attach to the left and right earlobes; each clip has two disposable pads that will be soaked with saline (to promote conductivity between the electrodes and skin). A single CES device labeled THRESHOLDING will always be used for this phase; this device will always be *active*. The device will be powered on and set to 0.5Hz at the lowest possible intensity (50 μ A). Participants will be told that we will increase the intensity by a very small amount every 30 seconds and ask them to answer each of the questions on the CES side effect questionnaire. At each 30-second interval, the experimenter will increase the stimulation intensity by 50 μ A.

If a participant has at least one symptom at 3 or higher (i.e., ≥ 3 in the Presence and Intensity section), *and* they believe it is "possibly" or "definitely" related to the stimulation (i.e., ≥ 3 in the Relation to Stimulation section), we will immediately stop the thresholding procedure. The stimulation intensity achieved will then be recorded by the experimenter.

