During the cognitive testing, if an incorrect response is provided by participants (e.g., > 45° absolute angular error during the spatial orienting task, incorrectly firing upon a friendly or incorrectly letting an enemy pass during the decision-making test), the system will automatically trigger a torso shock. The shock belt will be set at level 3, which (in our previous studies) participants tend to find uncomfortable and stressful, but not painful. If participants cannot tolerate the shock and ask for it to be disabled, we will pause data collection and give them a 5-minute rest period and ask whether they would like to try it again. If they respond *yes*, we will resume data collection (and repeat this rest-retry procedure as necessary). If they respond *no*, we will ask whether they are willing to be rescheduled and try again on another day; if they respond *no*, we will not reschedule. If they respond *yes*, we will reschedule the participant for another session. If during two consecutive sessions they cannot tolerate the shock, they will be dismissed from the study.

Upon completion of testing, participants will return to the private seating area, where they will complete the additional saliva sampling and STAI-S.

3. Saliva Sampling: Participants will provide saliva samples using the Salivabio Oral Swab (SOS) method from Salimetrics. This sampling method involves participants placing a hygienic absorbent swab under their tongue for 2 minutes, and then placing the swab into a vial. The advantage of the SOS method is that participants can do it entirely independently (opening the swab package, placing the swab under the tongue, removing swab from mouth, placing swab in the vial, closing the vial) and without direct contact from the experimenter. Using this method, saliva samples will be taken immediately prior to Questionnaires, immediately prior to Cognitive Testing Under Stress, immediately following Cognitive Testing Under Stress (accompanied by emotional state questionnaires), and at 20-minutes, 40-minutes, and 60-minutes after. In this manner, we will collect a total of 5 saliva samples during this Baseline session.

After completing this series of saliva samples, questionnaires, and tasks, participants will be briefed on the CES session procedures. Participants will then be released for the day. Overall, we expect the Baseline session to last approximately 3 hours, as detailed in the below example schedule:

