0800-0815	Questionnaires (daily checklist, STAI-S/T, demographics)
0815-0820	CES Thresholding
0820-0825	Saliva Sampling
0825-0900	Criteria Learning
0900-0920	Don Bioharness & Shock Belt; Don & Calibrate Eye Tracking Glasses & Rifle
0920-0945	Cognitive Testing Under Stress
0945-0950	Saliva Sampling & STAI-S
1005-1010	Saliva Sampling & STAI-S
1025-1030	Saliva Sampling & STAI-S

1045-1050	Saliva Sampling & STAI-S
1050-1100	CES Session Familiarization
1100	Dismissal

The CES Sessions

Participants will then return to the laboratory at CABCS or visit the laboratory at the DEVCOM Soldier Center on a daily basis (Monday through Friday) for up to six consecutive weeks, or until they achieve a total of 20 sessions (whichever occurs first). They will be scheduled at a semi-consistent time every day (i.e., in morning or afternoon), and complete a session expected to last about 30-60 minutes. During each session, participants will complete the daily participant questionnaire, the STAI-S, a CES stimulation period involving Active or Sham stimulation, a CES secondary administration (as needed), and the STAI-S.

If a participant answers 3 or higher on any question on the daily participant questionnaire, they will be rescheduled for a different day. If they report 3 or higher on any of the questions for two consecutive sessions, they will be withdrawn from the study.

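### Protocol Section 6.0 lists six saliva samples but counts five, and its example timetable has no swab or STAI-S just before stress, where the SAP takes its pre values

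*Protocol*

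**What the plan says.** **Protocol, Section 6.0, Saliva Sampling (item 3).** The text fixes two collection times before stress: "saliva samples will be taken immediately prior to Questionnaires, immediately prior to Cognitive Testing Under Stress". It adds one "immediately following Cognitive Testing Under Stress (accompanied by emotional state questionnaires") and three more at 20, 40 and 60 minutes. The next sentence totals these: "In this manner, we will collect a total of 5 saliva samples during this Baseline session".

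**Protocol, Section 6.0, Baseline timetable.** The session is set out "as detailed in the below example schedule". The 0800-0815 row reads "Questionnaires (daily checklist, STAI-S/T, demographics"). Thresholding follows at 0815-0820, a swab at 0820-0825, learning at 0825-0900, then "Don Bioharness & Shock Belt; Don & Calibrate Eye Tracking Glasses & Rifle" at 0900-0920, and testing at 0920-0945. Joint swab and STAI-S slots begin at 0945, 1005, 1025 and 1045.

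**Protocol, Section 6.0, STAI-S.** The opening of Testing Day 1 says "Participants will first complete the demographics form, daily participant questionnaire, and emotional state (STAI-S, STAI-T; see Appendix A) questionnaires". The Baselining paragraph asks for saliva and STAI-S before, during and after the learning and testing phases, without times. After stress the text is clear: "Upon completion of testing, participants will return to the private seating area, where they will complete the additional saliva sampling and STAI-S".

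**Protocol, Section 6.0, Follow-up.** The procedures are those of Baseline, less thresholding.

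**SAP.** The Manipulation Check section compares alpha amylase, cortisol and STAI-S at Baseline by paired t-tests. The pre value is defined as taken right before stress exposure, and the comparison value is the one taken straight after. The ANOVAs for alpha amylase, cortisol and STAI-S use a five-level Time factor: pre-task, 0, 20, 40 and 60 minutes.

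**The concern.** The stated total does not match the list that it sums. The conflict concerns the sample that serves as the reference value for every stress response in saliva.

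The timetable does not resolve it. Its one pre-stress swab comes after the questionnaires and thresholding, so it is not the arrival sample in the text. It comes before learning and equipment fitting, so it is not the pre-testing sample either. The timetable nevertheless has exactly five swabs and five STAI-S entries. A team working from it could fill the SAP's five Time levels without noticing that the first level is not what the SAP describes.

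The manipulation check would suffer most. It is meant to show that stress exposure moved the markers. Measured from the timetable's pre values, the change would also include learning to criterion and being fitted with the shock belt. This matters here because Protocol Section 2.0 reports that the team's previous stress induction moved SAM but not HPA measures, and shock intensity was raised in order to move both.

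**Working it through.** **1. Count of saliva samples per stress session**

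| Source | Before stress | After stress | Total |
|---|---|---|---|
| Section 6.0, list in the text | 2 | 4 (0, 20, 40, 60 min) | 6 |
| Section 6.0, stated total | – | – | 5 |
| Section 6.0, example timetable | 1 (0820) | 4 (0945, 1005, 1025, 1045) | 5 |
| SAP, Time factor | 1 (pre-task) | 4 (0, 20, 40, 60 min) | 5 |

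The stated five is reproduced by the timetable (1 + 4) and by the SAP (1 + 4), but not by the list it sums (2 + 4 = 6).

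**2. Where the conflict lies.** Timetable offsets from the end of testing at 0945 are 0, 20, 40 and 60 minutes. These agree with the text and with the SAP, so the conflict is confined to the pre-stress samples.

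**3. Gap from the scheduled pre sample to the start of testing (0920)**

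- Swab: ends 0825; 0825 to 0920 = 55 minutes.
- STAI-S: block ends 0815; 0815 to 0920 = 65 minutes.

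**4. What the pre-to-0-minute change in saliva would span.** From 0825 to 0945 is 80 minutes: 35 of learning (0825-0900), 20 of fitting and calibration (0900-0920) and 25 of testing (0920-0945). So 35 + 20 = 55 of the 80 minutes are not testing. No swab or STAI-S is scheduled in that window.

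**5. STAI-S entries.** The timetable has one in the 0800-0815 block and four after stress, making five, against five SAP Time levels. On the timetable alone, the pre-task level can only be the questionnaire completed on arrival.

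**6. Measures not affected.** For heart rate, HRV, respiration and tonic pupil diameter, the SAP takes the pre-stress value from the last minute before the tasks, so the swab and STAI-S timetable does not enter.

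No effect size is calculated, because the documents give no input on how far these markers drift during learning or fitting.

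**The case against.** The strongest reply is that the timetable is labelled an example, while the text is the instruction. The text requires a swab right before testing, and that swab plus the four later ones supplies all five SAP time points. The arrival swab would then be an extra that the SAP does not analyse. This stands as far as it goes: a reader might infer from the timetable that no immediate pre-stress saliva sample is planned, and the documents do not support that. What remains is that the count is wrong on this reading, the SAP does not mention the second pre-stress swab, and the only timetable staff have for this session omits the swab that the analysis needs.

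For STAI-S, the Baselining paragraph permits a questionnaire between learning and testing. That is also true, so this is an unspecified slot and not a direct contradiction. Still, no explicit slot exists there.

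One might also shorten the gaps to 35 and 45 minutes by counting stress from 0900, since the protocol describes belt fitting under the Cognitive Testing heading. The SAP's heart-rate sentence equates stress exposure with the three tasks and uses the same term for the other markers, so 55 and 65 minutes are the relevant figures.

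Finally, a reader might infer that the comparison of Active with Sham is biased. Nothing in the documents supports this: both groups follow the same timetable, and the hypotheses are all between groups.

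**Conclusion.** The point holds as an internal inconsistency with a conditional consequence. The miscount (six listed, five stated) and the missing slots are certain on the face of the documents. Which of the list or the total is in error cannot be settled from them.

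The consequence rests on one assumption: that sessions follow the example timetable. If so, the pre value falls 55 minutes (saliva) and at least 65 minutes (STAI-S) before testing instead of right before it. The three Baseline manipulation checks on alpha amylase, cortisol and STAI-S would then not isolate the stress exposure, and the pre-task level of the Time factor would be mislabelled in both sessions, because Follow-up repeats the Baseline procedures. If sessions follow the text, the saliva analysis is as the SAP describes and only the count, the unused arrival sample and the STAI-S slot need attention.

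This should be corrected, but it does not undermine the trial's main comparison.

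**What to change.** 1. Use one sampling list in the Section 6.0 text, the timetable and the SAP, with a correct count of five or six.
2. In both sessions, schedule a swab and a STAI-S after criterial learning and just before testing, and state whether they come before or after equipment fitting. After fitting, the value may already reflect anticipation of shock, and the participant is instrumented. Before fitting, the sample is 20 minutes from the start of testing on the present timetable. The sponsor should choose and say which is meant.
3. In the SAP, name that sample as the pre-task value. If an arrival swab is kept, say how it will be used.
4. The SAP is dated May 2025 and the protocol was approved in April 2023, so sessions may already have been run. In that case, report the actual minutes between each pre sample and the start of testing (for example, median and range), and drop the description of these values as taken right before stress where it is not true.

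**Cost.** With five samples, the scheduled swab is moved: no extra tubes. The 5 minutes freed at 0820-0825 cover a 5-minute joint swab and STAI-S slot, so net scheduled time is about zero. With six, add one tube and about 5 minutes per session: 40 completers × 2 sessions = 80 tubes, plus those from participants who do not complete. Either way there is one more STAI-S per session and a brief pause before testing. Step 4 needs only recorded times and a text edit.
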